5.4 Medical History

Medical history (i.e. condition no longer present), concomitant diseases (i.e. condition still present) and ADAMTS13 activity at admission will be listed (see Section [16.1](#)). Separate listings will be presented for general medical history and for TTP history.

5.5 Prior and Concomitant Medications

5.5.1 Analysis

Any concomitant medication taken during the study will be recorded in the eCRF.

All therapies are coded using the latest WHO-DRUG version, no Anatomical therapeutic chemical classification system (ATC) selection is performed.

Based on their start and stop date, previous and concomitant therapies will be reported in each analysis period during which they were applied (i.e. a non-treatment-emergent allocation). This implies that each therapy can be reported more than once. The analysis periods are defined in Section [4.4.1](#).

If a therapy record misses components of its start and/or stop dates (day and/or month and/or year), a worst-case allocation will be applied:

- In case of partial start or stop dates, the concomitant therapy records will be allocated to analysis phases or (sub)periods using the available partial information, without imputations. If, for example, only month and year are available, these will be compared to the month and the year of the phases, and the concomitant therapy record will so be allocated to the analysis phase(s) or (sub)period(s) where these date parts match.
- In case of a completely missing start date, the concomitant therapy will be considered as having started before the trial.
- In case of a completely missing end date, the concomitant therapy will be considered as ongoing at the end of the trial.

Previous and concomitant therapies will be tabulated by generic term and by analysis period (DB treatment daily PE period, DB treatment post-daily PE period, OL treatment daily PE period, OL treatment post-daily PE period, overall treatment period, follow-up period, overall study period). Multiple records of the same generic term for the same subject will be counted only once. The table will therefore present subjects, not occurrences. The tables are sorted by decreasing frequency (overall). Immunosuppressive (including rituximab) and non-immunosuppressive concomitant therapies will be tabulated separately. A separate tabulation by analysis period will be made to summarize the number and proportion of subjects who received concomitant antithrombotic therapies (ATC codes starting with B01A) and the number and proportion of subjects to whom transfusions have been given.

The duration of corticosteroids use and the cumulative dose of corticosteroids during the overall treatment period will be summarized by treatment group. The treatment groups for this analysis will be defined as:

- Caplacizumab + OL Caplacizumab
- Placebo + OL Caplacizumab

This definition implies that subjects will be analyzed according to their initial treatment group, both before and after switch to open-label caplacizumab.

Different types of corticosteroids will be converted to Prednisolone equivalent doses before calculating the cumulative dose of corticosteroids. The cumulative dose will be given in mg/day (Please refer to Appendix C section [17.3](#) for more details).

A detailed list of tables and listings can be found in Section [14.1](#) and Section [16.1](#), respectively.

5.6 Exposure to Study Medication

Extent of exposure will be analyzed descriptively by treatment group and overall based on the safety population. The following exposure parameters will be considered:

- DB treatment duration (days) = (date of last administration – date of first administration within the DB treatment period + 1)
- OL treatment duration (for switchers only) (days) = (date of last administration – date of first administration within the OL treatment period + 1)

- Total treatment duration (days) = (date of last drug administration – date of first drug administration + 1 day). The treatment groups Caplacizumab + OL Caplacizumab and Placebo + OL Caplacizumab will be considered for this analysis. Subjects will thus be analyzed according to their initial treatment group, both before and after switch to open-label caplacizumab.
- Compliance, calculated as (number of study drug administrations received / number of study drug administration planned)*100% will be tabulated by (sub)period

The number and proportion of subjects with treatment extensions will be summarized by treatment group (Caplacizumab, Placebo, OL Caplacizumab).

A detailed list of tables and listings can be found in Section 14.1 and Section 16.1, respectively.

6 EFFICACY

6.1 Primary efficacy endpoint evaluation

6.1.1 Primary efficacy analysis

The primary endpoint of the study is: time to platelet count response. Platelet count response is defined as initial platelet count $\geq 150 \times 10^9/L$ with subsequent stop of daily PE within 5 days. It refers to the first time both conditions, platelet count above $150 \times 10^9/L$ and the stop of dPE within 5 days, are met; so it is not necessarily the first time the platelet count goes above $150 \times 10^9/L$.

Only data from the double blind daily PE period up to the cut-off point will be used for the analysis of the primary endpoint. The data cut-off point is defined by either:

- 45 days of daily PE after the start of study drug,
- The stop of daily PE
- The stop of study treatment drug,

[figure not shown]
[figure not shown]
[figure not shown]
whichever occurs first.

[figure not shown]
[figure not shown]
[figure not shown]
[figure not shown]
The time to platelet count response is calculated as the time of the event/censor – time of first i.v. loading dose of study drug after randomization + 1 minute. The time to response will be represented by number of days with two decimal digits.

[figure not shown]
[figure not shown]
[figure not shown]
For the platelet count measurements with missing time part, the missing sample time will be imputed using the first dosing time minus 1 minute for the subject.

Depending on the time of platelet count $\geq 150 \times 10^9/L$, the time of stop of daily PE and the stop of study drug treatment, different potential scenarios for the event time and censoring of observations are possible. These are presented in Table 2.

Table 2: Censoring and event plan

Scenario	Response	Censored	Time to event / censoring time (days)	Graphical representation (grey bar represents dPE)
1) Initial platelet count $\geq 150 \times 10^9/L$ at day x with subsequent stop of dPE within 5 days, platelet count stays $\geq 150 \times 10^9/L$ as of day x ($x \leq 45d$)	Yes	0	x	
2) Initial platelet count $\geq 150 \times 10^9/L$ at day x with subsequent stop of dPE within 5 days. Platelet count dropped below $150 \times 10^9/L$ between day x and stop of dPE on day y ($y \leq 45d$) and was not $\geq 150 \times 10^9/L$ by the stop of dPE	Yes	0	x	
3) No platelet count $\geq 150 \times 10^9/L$ within 45 days of continuous dPE	No	1	45	

4) No platelet count $\geq 150 \times 10^9/L$ and at day x subject early terminated with no initial platelet count response ($x \leq 45d$)	No	1	x	
5) Platelet count $\geq 150 \times 10^9/L$ (at day x) after being below $150 \times 10^9/L$, with subject early terminated within 5 days while on dPE	Yes	0	x	
6) Stop of dPE at day x without platelet count $\geq 150 \times 10^9/L$ ($x \leq 45d$)	No	1	x	
7) Stop of dPE at day x without platelet count $\geq 150 \times 10^9/L$ and platelet count $\geq 150 \times 10^9/L$ at day x+y ($x \leq 45d$, $y > 0d$)	No	1	x	

8) Platelet count $\geq 150 \times 10^9/L$ at day x with stop of dPE 5+y days later ($y > 0$), platelet count stays $\geq 150 \times 10^9/L$ as of day x ($x+y \leq 45$ days)	Yes	0	x+y	
9) Platelet count $\geq 150 \times 10^9/L$ at day x with stop of dPE 5+y days later ($y > 0$), platelet count has not been $\geq 150 \times 10^9/L$ between day x+y and day x+y+5 ($x+y+5 \leq 45$ days)	No	1	x+y+5	
10) Study drug withdrawn at day x with no Platelet count $\geq 150 \times 10^9/L$, and the subject early terminated y days later ($y > 0$, $x+y \leq 45$ days). The subject was still on dPE until early termination	No	1	x	

Time to platelet count response in the caplacizumab arm and placebo arm will be compared by conducting a two-sided stratified Log-rank test based on a Kaplan-Meier (KM) analysis, with severity of neurological involvement (according to the GCS, stratification factor used in randomization: $\leq 12 / 13-15$) as stratification factor. The resulting p-value will be compared with the significance level α of 5%. In case the p-value is smaller than 0.05 and the estimated median time to platelet count response in the caplacizumab treatment group is smaller than in the placebo treatment group, a significant reduction of time to platelet count response by caplacizumab will be concluded and the primary endpoint will have been met.

This analysis will be performed on the ITT population. Subjects will be analyzed according to the treatment to which they were assigned. Switch of subjects who experience a recurrence of TTP during the study to open-label caplacizumab will not affect the primary efficacy endpoint analysis as a recurrence can only occur after platelet count response, i.e. initial platelet count $\geq 150 \times 10^9/L$ with subsequent stop of daily PE within 5 days, has been reached.

Besides the p-value, the table on the primary analysis will include standard KM estimates such as the median, 25% percentile and 75% percentile of the time to platelet count response by treatment group with associated 95% CIs, as well as the number of events and the number of censored observations. This summary will be presented both by GCS category, and overall, i.e. unadjusted by GCS category.

The KM estimates will also be presented graphically, unadjusted by GCS category.

The data will also be analyzed using a Cox proportional hazards regression model with time to platelet count response as dependent variable, and treatment group and GCS category as independent variables. The hazard ratio (HR) from the Cox model will be reported along with 95% CI in the table. The adequacy of the Cox model will be tested using the graphical and numerical methods of Lin, Wei, and Ying (1993). The proportional hazards assumption will be checked by using a transform of the martingale residuals known as the empirical score process. The assumption will be tested graphically by plotting for each covariate the simulated score processes, representing score processes under the proportional hazards assumption, and comparing them to the observed score process. In addition, a supremum test will be reported to assess the proportion of simulated score processes that yielded a maximum score larger than the maximum observed score process. A very small proportion (p-value) suggests violation of proportional hazards. In case the proportional hazards assumption does not hold, effect of potential confounding factors such as use of rituximab, disease severity at baseline, and baseline ADAMTS13 activity levels will be explored using stratified proportional hazards model(s), if feasible (i.e. depending on number of subjects in strata).

The following sas code will be used as starting point for the primary analysis.

For the Kaplan-Meier (KM) analysis:

```
proc lifetest data=inputdata;
  time aval*cnsr(1);
  strata trt01p trt01pn / test=(logrank);
  ods output quartiles=quartile CensoredSummary=censor;
run;

where
INPUTDATA is the input dataset
AVAL is the time to the event variable,
CNRS is 0 (subjects with events) or 1 (subjects without no event,
i.e. subject censored)
TRT01P and TRT01PN are respectively the categorical and numeric
versions of the planned treatment groups used for the subjects during
the DB treatment period
```

For the stratified Log-rank test:

```
proc lifetest data=inputdata;
  time aval*cnsr(1);
  strata gcsscosc / test=(logrank);
  test trt01pn;
  ods output LogUniChiSq=logrank;
run;
```

CONFIDENTIAL

where
 INPUTDATA is the input dataset
 AVAL is the time to the event variable,
 CNRS is 0 (subjects with events) or 1 (subjects without no event,
 i.e. subject censored)
 TRT01PN is the numeric version of the planned treatment groups used
 for the subjects during the DB treatment period
 GCSSCOSC is the Glasgow Coma Scale Category for each subject

For the Cox proportional hazards regression model:

```
proc phreg data=inputdata;
  class TREATMENT (ref="1") GCS (ref="1");
  model aval*cnsr(1)= TREATMENT GCS / ties=efron risklimits type3;
  estimate "TREATMENT" TREATMENT 1 / cl;
  estimate "GCS" GCS 1 / cl;
  assess ph / crpanel resample;
  ods output ParameterEstimates=parestimate
  ProportionalHazardsSupTest=proptest Estimates=estimate;
run;
```

where
 INPUTDATA is the input dataset
 AVAL is the time to the event variable,
 CNRS is 0 (subjects with events) or 1 (subjects without no event,
 i.e. subject censored)
 TREATMENT is the numeric version of the planned treatment group used
 for the subjects during the DB treatment period
 GCS is the Glasgow Coma Scale Category for each subject

A detailed list of tables, listings and figures can be found in Section [14.2](#), Section [16.2](#) and Section [15.1](#), respectively.

[figure not shown]
[figure not shown]
[figure not shown]
Time to platelet count response will be measured from the time of the first i.v. loading dose of study drug after randomization. In the KM analysis an observation will be censored if the defined time interval of 45 days after first administration of study drug is not met, due to any cause (e.g., endpoint not being reached within this time interval or subject lost to follow-up).

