^a General medical history and TTP-specific medical history. The result of an ADAMTS13 activity test performed as per standard of care upon admission will be collected in the eCRF, if available.

^b To be assessed within 2 hours prior to randomization.

^c Bleeding assessment is a clinical assessment of signs and symptoms of bleeding (e.g., petechiae, hematuria, epistaxis, meno-metrorrhagia, bruises) performed by the Investigator.

^d Only for women of childbearing potential. Pregnancy test (urine or blood) will be assessed locally.

^e Samples for platelet count, blood smear and serum creatinine will be assessed by a local laboratory (values of samples taken as part of standard of care can be used, if available).

Ablynx NV	Clinical Trial Protocol ALX0681-C301	
Pharm-Olam Ltd.	Final version 3.0	

Table 2: Time and events schedule: Daily PE period ^a

Study Visit	Day 1 (Baseline)	Day 2	Day 3	Day 4	DAILY from Day 5 to end of daily PE	WEEKLY ^b on Day 8, 15, ... (± 1 day)
Complement C5a and C5b-9 (initial daily PE period only)	x					
Randomization	x					
Study drug administration ^c	x	x	x	x	x	x
Plasma exchange + corticosteroids ^d	x	x	x	x	x	x
Neurologic assessments ^e	x	x	x	x	x	x
SMMSE	x	x	x	x	x	x
Clinically significant TTP event	x	x	x	x	x	x
Bleeding assessment ^f	x	x	x	x	x	x
Physical examination	x					x
Height and weight (initial daily PE period only)	x					
Vital signs ^g	x					x
12-lead ECG ^h	x	x	x	x		
Adverse events						→
Concomitant medication						→
Platelet count ^j	x	x	x	x	x	x
Blood smear ^j	x					
Clinical laboratory analyses ⁱ	x					x
Organ damage markers ^k	x	x	x	x	x	x
ADAMTS13 activity	x					
PK	x	x	x			
PD parameters ^l	x	x	x			
Immunogenicity (ADA) ^m	x					

^a The following guidance with regard to timing of assessments planned at a single visit should be followed: 1) ECG and vital signs should be assessed prior to blood sampling, 2) assessments should be done prior to start of PE (and on Day 1, prior to the i.v. dose administration), and 3) s.c. study drug should be dosed after end of the day's PE.

This time and events schedule is also applicable for open-label caplacizumab in case of a first exacerbation or relapse (relapse during the treatment extension period). Of note, complement (C5a and C5b-9) and height and weight are to be assessed at the initial daily PE period only.

^b All assessments to be done on Day 8, 15,... include assessments done on daily basis plus extra weekly assessments.

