3.3. TREATMENT OF SUBJECTS

Study drug treatment:

Daily PE period

- Loading i.v. dose: subjects will receive a single loading dose of 10 mg study drug by i.v. bolus injection from 6 hours to 15 minutes prior to the first PE done after randomization; also i.v. bolus of 10 mg caplacizumab (open label) will be given prior to the 1st PE for treatment of a first exacerbation during the 30-day post daily PE period or a first relapse during the treatment extension period (without a prior exacerbation).
- Daily s.c. dose: within 2 hours of completing each daily PE, a s.c. injection of 10 mg study drug will be administered daily throughout the full duration of PE treatment.

For more details on the study drug administration, please refer to section [3.3.5](#).

It is expected that subjects are hospitalized for the duration of the daily PE period. Exceptions should be discussed with the Medical Monitor.

30-day post-daily PE period

Daily s.c. administration of 10 mg study drug will continue for a period of 30 days after stop of daily PE. No adjustment to this period will be made for tapering of PE. Study drug should be administered at approximately the same time each day. Towards the end of the daily PE period and when hospital discharge is foreseen, subjects (or caregiver) should be trained in the s.c. self-administration of the study drug under the supervision of the Investigator or designee to allow for self-administration when at home. After discharge from hospital, subjects or caregiver will need to be able to self-administer s.c. study drug. For more details, please refer to section [3.3.5](#).

Treatment extension period

Study drug treatment extension beyond the 30 days will be guided by a number of risk factors for relapse of the presenting TTP episode and must be accompanied by an optimization of the immunosuppressive treatment. Study drug treatment should be extended for subjects who in the opinion of the Investigator have persistent active underlying disease for additional 7-day periods with a maximum of 28 days. In parallel, optimization of the immunosuppressive treatment should be considered at least at the Week 3 visit of the 30-day post-daily PE period and may include reversal of corticosteroid tapering through increase or re-initiation of corticosteroid treatment, or start/continuation of other immunosuppressive treatment such as rituximab (to be used as per standard site practice).

Decision on treatment extension

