3.3.6. OTHER TREATMENT/MEDICATION ADMINISTERED IN THE STUDY

Standard of care treatment:

- PE with plasma (e.g., fresh frozen plasma, solvent detergent/viral-inactivated plasma, cryosupernatant) at 1 to 1.5 x estimated plasma volume daily as of randomization. PE [see section 3.1.1] should have been started prior to randomization with volume and intensity at the discretion of the Investigator. PE duration and whether desired volume is exchanged in one or more sessions within 24 hours is at the discretion of the Investigator, according to standard site practice. Note that the maximum time allowed between the start of first PE (i.e., PE administered prior to randomization) and the start of the first PE after randomization (i.e., the first on-study PE) is 24 hours.
- Once the platelet count is $\geq 150 \times 10^9/L$, daily PE should continue for at least 2 days.
- Tapering of PE after platelet count normalization is strongly discouraged and if considered, should be discussed with the Medical Monitor.

Information with regard to PE to be recorded in the eCRF will include: start time and end

time of that day's PE, number of sessions for the desired plasma volume, plasma volume (in L and in multiple of total plasma volume), plasma product name, plasma exchange technique, and specification with regard to single or pooled donor.

Corticosteroid treatment:

Corticosteroid treatment should be initiated/continued with (methyl)prednisolone or (methyl)prednisone regimen of at least 1 mg/kg/day i.v. or p.o. during the daily PE period and continued for the 1st week after end of daily PE. Afterwards corticosteroids may be tapered at the discretion of the Investigator, with the aim of being corticosteroid-free by Day 30 after cessation of daily PE as clinically indicated. At the Week 3 visit of the 30-day post-daily PE period, corticosteroid tapering should be reassessed based on ADAMTS13 activity data of the previous 2 visits and other clinical signs of underlying disease.

Other immunosuppressive treatment:

The use of other immunosuppressive treatment (e.g., rituximab) is allowed per standard site practice but should be considered in light of protocol required corticosteroid treatment.

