3.4.1.2. ASSESSMENT PERIOD

During the daily PE period, assessments should be performed at approximately the same time with frequency as detailed in the Schedule of Assessments.

⁺⁺⁺ Note that study drug administration can occur on Day 2 as a time window of 24 hours is permitted between the start of first PE (i.e., PE administered prior to randomization) and the start of the first PE after randomization (i.e., the first on-study PE), resulting in a possible time window between randomization and first study drug administration.

After the end of daily PE, subjects will return for ambulatory visits planned once weekly. All weekly visits should occur at the indicated week \pm 1 day.

Of note, as tapering of PE after platelet count normalization is strongly discouraged, visits in the 30-day post-daily PE period are linked to end of daily PE (not taking into account possible tapering).

All assessments will be performed as specified in the [Schedules of Assessments](#).

Unscheduled visits may be planned to assess, confirm, and follow up on clinically relevant AEs or laboratory abnormalities. Findings made during these unscheduled visits should be reported in the designated sections of the eCRF.

Missed visits:

All attempts should be made to follow the original visit schedule. If a subject misses a visit, he/she should come to the site as soon as possible after the planned missed visit.

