3.4.11. APPROPRIATENESS AND TIMING OF MEASUREMENTS

The assessments which will be made in this study are standard and generally recognized as reliable, accurate, and relevant.

The timing of all assessments is detailed in the [Schedules of Assessments](#).

During the daily PE period, samples for PK, PD, disease-related markers and safety will be obtained on the day itself and prior to PE (for Day 1, i.e., prior to the i.v. dose administration).

Following guidance with regard to timing of assessments planned at a single visit should be followed:

- 1) ECG and vital signs should be assessed prior to blood sampling, and
- 2) Assessments should be done prior to start of PE (and on Day 1, prior to the i.v. dose administration), and
- 3) s.c. study drug should be dosed after all other assessments have been performed (and during the daily PE period, s.c. study drug should be dosed after end of the day's PE).

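### Missing platelet sample times on later days are filled with the first-dose hour, although that day's PE start time is in the eCRF: a minor loss of accuracy in primary event times

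*SAP*

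**What the plan says.** SAP 6.1.1 addresses platelet counts that have a date but no time: "the missing sample time will be imputed using the first dosing time minus 1 minute for the subject". It does not limit this to Day 1. The same section counts the event time from the first dose, subtracting the "time of first i.v. loading dose of study drug after randomization + 1 minute", and presents the result in days to two decimals.

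The protocol fixes when samples are taken relative to PE and to the dose. Section 3.4.11 states: "Assessments should be done prior to start of PE (and on Day 1, prior to the i.v. dose administration"; footnote a of Table 2 in the Schedules of Assessments says the same. Section 3.4.1.2 adds that during the daily PE period "assessments should be performed at approximately the same time with frequency as detailed in the Schedule of Assessments". Under section 3.3 the loading dose is given "by i.v. bolus injection from 6 hours to 15 minutes prior to the first PE done after randomization".

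The clock time of each day's PE is collected. Protocol 3.3.6 states: "Information with regard to PE to be recorded in the eCRF will include: start time and end" time of that day's PE. SAP 6.1.1 does not use it.

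On the data window, SAP 6.1.1 states: "Only data from the double blind daily PE period up to the cut-off point will be used". The cut-off is the earliest of 45 days of daily PE, stop of daily PE and stop of study drug. No clock time is given for either stop.

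**The concern.** The hour of the first dose depends on when the patient was admitted, randomized and able to start the first on-study PE, which must begin within 24 hours of the start of the pre-randomization PE (Protocol 3.1.1). Protocol 3.1.2 itself describes an emergency care setting. From Day 2 the schedule may settle at another hour. The rule nevertheless carries the first-dose hour forward to every later sample without a time.

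For example, take a first dose at 20:00 on Day 1 and a qualifying count on Day 4 drawn at 07:00 before a 09:00 PE, with the time not recorded. The rule enters 19:59, and the event time becomes 3.00 days instead of 2.46.

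At stake is the accuracy of individual event times and of the Kaplan-Meier medians and quartiles. None of the sensitivity analyses in SAP 6.1.2 varies the imputed times, and no count of them is planned.

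**Working it through.** **1. The plan's own figures, as a base.** Inputs from SAP 3.2: medians 7 and 4.2 days (hazard ratio 4.2/7 = 0.6), two-sided 5%, 80% power, 10% drop-out in the first 10 days, 45-day horizon.
- Events (Schoenfeld): 4 × (1.960 + 0.842)² / (ln 0.6)² = 4 × 7.85 / 0.261 = 120.3, rounded up to 121. Power with 121 events is 80.2%.
- Drop-out hazard: η = -ln(0.9)/10 per day. Event probability with hazard λ = ln 2/median: λ/(λ+η) × [1 - exp(-45(λ+η))] = 0.897 (placebo) and 0.940 (caplacizumab), mean 0.918.
- Subjects: 121/0.918 = 131.7, so 132.

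The stated 132 subjects, 121 events and 80% all reproduce.

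**2. What the rule does to one event time.** Let d be the clock hour of the first dose, s the true clock hour of the sample, and k the number of calendar days after the dose date.
- Imputed: [24k + (d - 1 min)] - d + 1 min = 24k hours, exactly k.00 days.
- True (dropping the 1 minute): 24k + s - d hours.
- Error = d - s.

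In the example above, k = 3, d = 20 and s = 7. The imputed time is 72 h = 3.00 days, the true time is 59 h = 2.46 days, and the error is +13 h.

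**3. When the error is small.** If PE stays at the hour of the first on-study session, the imputed time is between 15 min + 1 min = 16 min and 6 h + 1 min = 6 h 1 min before that day's PE. That is consistent with sampling before PE.

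**4. Range under assumed clock times.** The documents give no clock hours. Assume s uniform on 07:00-10:00 (mean 8.5).

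| First dose assumed uniform over | Range of d - s | Mean of d - s |
|---|---|---|
| 00:00-24:00 | -10 to +17 h | 12 - 8.5 = +3.5 h (0.15 day) |
| 08:00-20:00 | -2 to +13 h | 14 - 8.5 = +5.5 h (0.23 day) |
| 12:00-24:00 | +2 to +17 h | 18 - 8.5 = +9.5 h (0.40 day) |

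These are errors per affected sample. The share of samples affected is unknown.

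**5. Effect on the test.** The settings were simulated with 2,000 trials each: 66 per arm, exponential times and drop-out as in step 1, detection at the next daily sample, unstratified log-rank test. The simulation standard error is about 0.9 percentage point for power and 0.5 for type I error.
- Shift alone, 0 to 100% of times missing: power 79.0-79.5%, against 79.1% with true times.
- Shift plus a cut-off at the clock time of the end of the last PE, assuming first doses after noon, 10% of responses on the last PE day, and PE ending 4 h after the sample hour:

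| Times missing | Events lost per trial | Power |
|---|---|---|
| 0% | 0 | 79.6% |
| 5% | 0.6 | 79.4% |
| 10% | 1.1 | 79.1% |
| 20% | 2.3 | 78.4% |
| 100% | 11.3 | 74.3% |

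- Type I error in that second setting (both medians 7 days): 5.0-5.5%, including 5.5% with no times missing.

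**6. Can the rule push a response past the cut-off?**
- 45 days: a sample 45 calendar days after the dose date is imputed at exactly 45.00 days, so it stays inside.
- Stop of daily PE: SAP 4.4.1, Table 1, starts the post-daily PE subperiod at 00:00 on the day after the switch, so the daily PE subperiod runs to 23:59 on the switch date. SAP 6.2.2 derives the time to stop of daily PE from dates only. On that footing a last-day sample stays inside whatever its imputed hour.

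**The case against.** The strongest defence is that the rule is a reasonable convention for once-daily samples. The first-dose time is itself a time before dosing and before PE, assessments are meant to be at about the same time each day, and the two 1-minute terms cancel so that imputed events fall on whole days. The first-dose hour is set before any treatment effect and under blinding, so the error should be alike in both arms. The 20:00 example is a chosen case, and the proposed anchor is also approximate: it would enter 08:59 for a sample drawn at 07:00. All of this stands. What remains is that the rule relies on PE keeping its first hour, which the documents do not assure, and that a closer anchor is already recorded.

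A reader might infer four stronger things, none of which the documents support.
- **That the rule contradicts sampling before PE.** It does not on Day 1, nor later if PE stays at a similar hour.
- **That last-day responders become censored failures.** This needs the stop of PE or of study drug to be applied by clock time, which Table 1 and SAP 6.2.2 do not suggest. A first count of at least 150 × 10⁹/L on the last PE day is also not expected, because the protocol has daily PE continue for at least 2 days after that count. Moreover, the SAP 6.1.2 analysis that drops the PE-stop requirement would still count such a patient as a responder.
- **That the whole date-time is replaced, giving an event time of 0.** The sentence concerns a missing time component and leaves the sample date alone.
- **That the error removes a share of the treatment difference.** It applies per affected sample in both arms, so it cannot be set against the assumed 2.8-day difference in medians (7 - 4.2).

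**Conclusion.** The point holds as a minor one. From Day 2 on, the rule can misplace a primary event time by hours: about -10 to +17 h if samples are drawn at 07:00-10:00 and first doses fall at any hour, with a mean of 0.15 to 0.40 day per affected sample depending on the assumed dosing hours. An error of that size is visible in an endpoint given to two decimals of a day, but its effect on the reported medians depends on the share of missing times, which the documents do not give.

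The comparison between arms is not at risk. Power and type I error are essentially unchanged by the shift. Even under the unsupported clock-time cut-off, 5-20% missing times cost 0.6 to 2.3 events and at most 1.2 points of power (79.6 - 78.4). These results rest on the assumed clock hours, on missing times being unrelated to arm, and on an unstratified test.

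**What to change.** In SAP 6.1.1, replace the imputation sentence with a rule that:
- fills only the time part and keeps the recorded sample date;
- on a day with PE, uses the recorded start of that day's first PE session minus 1 minute;
- on Day 1, keeps first dose minus 1 minute;
- on a day without PE, uses the subject's median recorded sample time.

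Add that the stop-of-PE and stop-of-drug cut-offs apply at 23:59 of the date, in line with Table 1, and report the number of imputed sample times by arm.

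The cost is a few lines of text and a little programming, with no new data collection. The imputed time remains an approximation, but in the example the error falls from about 13 hours (19:59 for 07:00) to about 2 hours (08:59 for 07:00).
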